#### Statistical analysis

Means and standard deviations of subject demographic data, as well as pain, functional, and treatment satisfaction scores will be calculated. Intergroup differences will be assessed by t test for numerical data and Chi Square or Fisher Exact test for categorical data. Regression modeling will be implemented using ANOVA to assess for patient traits and characteristics that increase the likelihood of efficacy using one technique as opposed to the other.

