## **Study design:**

### **Prospective, randomized, comparative trial**

Patients will be randomized to group #1 or #2 based on a random computer-generated schedule.

Group #1: Transforaminal cervical ESI with dexamethasone sodium phosphate 1.5 mL (10mg/mL) and 1 ml 1% lidocaine (total volume 2.5 mL).

Group #2: Catheter-targeted ESI via interlaminar access at the C7-T1 level with triamcinolone acetonide 2 mL (40mg/mL) and 1 ml 1% lidocaine (total volume 3 mL).

Dexamethasone will be used in the transforaminal group, while triamcinolone will be used in the catheter-based group as this represents the standard of care for performing these injections, consistent with current safety recommendations.

Adults who are eligible and scheduled to have an epidural steroid injection for cervical radicular pain at the University of Utah Orthopaedic Center will be approached by authorized research personnel. All eligible patients will be offered to participate in the study and all patients will sign a written informed consent form before proceeding and will also be consented for the procedure. Participating in the study is voluntary. The patients may choose not to enroll in the research. Patients will be presented with the same options of treatment whether they enroll or decide not to.

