#### **Data Collection:**

An electronic data collection sheet (via iPad) will be used to record all pre-procedure data (see data collection sheet):

- 1) Age (years).
- 2) Sex.
- 3) Height (cm).
- 4) Weight (Kg).
- 5) Duration of pain (weeks).

- 6) Location of cervical radicular pain based on clinical diagnosis: C2, C3, C4, C5, C6.
- 7) Radiologic diagnosis based on MRI of the Cervical Spine.

Before an initial injection, the following measures will be obtained:

- 7) NRS for pain; separate scores for neck pain and for arm pain
- 8) Neck Disability Index (NDI-5)
- 9) Medication Quantification Scale (MQS III) score
- 10) Daily opioid use in morphine equivalents

Immediately after injection the following will be obtained:

- 11) Fluoroscopy time
- 12) Post-injection NRS pain score; separate scores for neck pain and for arm pain
- 13) Adverse events, if they occurred

At intervals of 2 weeks, 1 month, 3 months, 6 months, and 1 year after injection, outcome measurements will be repeated. The Patient Global Impression of Change (PGIC) and a patient satisfaction score (five-point Likert scale: 1, very dissatisfied; 2, dissatisfied; 3, neither satisfied nor dissatisfied; 4, satisfied; and 5, very satisfied) will also be recorded. A single researcher blinded to group assignment collected all follow-up assessments in person, by e-mail, by telephone, or by mailed questionnaire.

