#### **Data Analysis Plan**

The primary outcome will be the proportion of participants with 50% or greater reduction in neck and arm pain on the NRS pain score at the 1-month follow-up assessment. Secondary outcomes included reduction in median NRS pain score (both neck pain and arm pain), NDI-5, MQS III, opioid consumption in daily morphine equivalents, PGIC score, and satisfaction score. Secondary outcomes will also be defined based on categorical “responder analysis” definitions of important clinical change given the National Institutes of Health recommendation for responder analysis in the assessment of therapeutic spine pain interventions. The responder analysis will include the proportion of patients with 30% or greater improvement on the NDI-5, a PGIC score less than 3 (indicating “improved” or “very much improved”), a 6.8 or greater point reduction on the MQS III score (equivalent to approximately 10 daily morphine equivalents), and the proportion of participants who undergo surgical spine surgery.

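### The primary responder comparison is unadjusted and makes no use of recorded prognostic baseline values; pre-specified adjustment would add some power at almost no cost, and baseline data should be described without tests

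*Combined protocol and SAP*

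**What the plan says.** The Data Analysis Plan defines the primary outcome as "the proportion of participants with 50% or greater reduction in neck and arm pain on the NRS pain score at the 1-month follow-up assessment", a binary variable for each participant.

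The Statistical analysis section begins: "Means and standard deviations of subject demographic data, as well as pain, functional, and treatment satisfaction scores will be calculated". The next sentence is "Intergroup differences will be assessed by t test for numerical data and Chi Square or Fisher Exact test for categorical data". No covariate is named, and no sentence separates baseline variables from outcomes. The only regression is an ANOVA-based model intended "to assess for patient traits and characteristics that increase the likelihood of efficacy using one technique as opposed to the other". That is a search for effect modifiers, not an adjusted treatment comparison.

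Under Study design, "Patients will be randomized to group #1 or #2 based on a random computer-generated schedule". No stratification factor is named there or under Subjects.

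The Data Collection section gives two baseline lists. The first, introduced by words saying that an electronic sheet "will be used to record all pre-procedure data (see data collection sheet"), has seven items: age, sex, height, weight, pain duration, pain location and "Radiologic diagnosis based on MRI of the Cervical Spine". The second, under "Before an initial injection, the following measures will be obtained", has five: neck NRS, arm NRS, NDI-5, MQS III and daily opioid use.

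**The concern.** There are two linked issues.

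**Unused information.** The trial records variables before the first injection that may well predict who responds, such as baseline pain and its duration. The primary test ignores them as covariates. The trial is small and does not stratify, so adjustment could recover some precision from the same patients. The Power Analysis states no alpha, power, response rates or effect size, so nothing shows that there is power to spare.

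**Tests on baseline data.** If the test rule covers the demographic data in the sentence before it, the plan will produce p-values for differences that, under randomisation, can only be due to chance. Such p-values do not show whether an imbalance matters for the outcome. The plan also does not say what would follow from a small one.

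**Working it through.** **1. The plan's own figure.** Power Analysis: 40 per group, 20% attrition, 100 recruited. 40 / (1 - 0.20) = 50 per group, or 100 in total, which reproduces. The 40 itself cannot be derived, because the section gives no alpha, power or effect size. The attrition applies to 6 months and the primary outcome to 1 month, so 40 to 50 per arm are likely to be evaluable.

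**2. Unadjusted power.** Assumed: two-sided alpha 0.05 and a 50% response rate in one arm. With p̄ the mean of the two rates p1 and p2,

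power = Φ{ [ |p1 - p2| - 1.96 √(2p̄(1-p̄)/n) ] / √([p1(1-p1) + p2(1-p2)]/n) }.

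For 50% vs 70% and n = 40: (0.20 - 1.96 × 0.1095) / 0.1072 = -0.137, so power is 44.5%.

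| Rates | 40 per arm | 50 per arm |
|---|---|---|
| 50% vs 70% | 44.5% | 53.3% |
| 50% vs 75% | 64.1% | 74.0% |
| 50% vs 80% | 81.6% | 89.4% |

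At 40 per arm, 80% power from a 50% rate needs a difference of about 30 points.

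**3. Power with adjustment (simulation).** An uncorrected chi-square test was compared with a logistic model of responder status on arm plus baseline covariates. Covariate strength is assumed throughout.

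- *50% vs 70%, 40 per arm, one prognostic and two useless covariates:* about 45% unadjusted, about 48-55% adjusted as the covariate goes from moderately to strongly prognostic. There is no loss when none is prognostic. Type I error is about 5-6% either way.
- *50% vs 70%, covariate strength expressed as a c-statistic:* at 40 per arm, 46.0% to 48.0% (c = 0.66) and 46.2% to 52.8% (c = 0.74). At 50 per arm, 52.4% to 56.4% (c = 0.66) and 53.6% to 60.3% (c = 0.73).
- *40 per arm, one covariate, 3,000 runs per row:*

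| Log-odds per SD | 50% vs 75%: unadjusted → adjusted | 50% vs 80%: unadjusted → adjusted |
|---|---|---|
| 0 | 63.8% → 64.3% | 82.2% → 82.9% |
| 0.5 | 65.1% → 68.6% | 81.8% → 83.8% |
| 0.8 | 64.5% → 70.4% | 82.0% → 86.7% |
| 1.2 | 64.3% → 76.2% | 81.9% → 90.1% |

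In these single-covariate runs the null rejection rate was 5.3-5.6% unadjusted and 4.7-5.4% adjusted. The Monte Carlo standard error at 45% with 3,000 runs is √(0.45 × 0.55 / 3000) = 0.9 points.

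**4. Baseline tests.** The two lists give 7 + 5 = 12 items. At 0.05 each, 12 × 0.05 = 0.6 false positives are expected. If the items are independent, P(at least one) = 1 - 0.95^12 = 46.0%. With equal correlation between items (simulated, 50 per arm), it is about 43% at rho 0.2, 37% at 0.4 and 27% at 0.6. If only age, sex, height and weight are tested, it is 1 - 0.95^4 = 19%. With neck NRS, arm NRS and NDI-5 added, it is 1 - 0.95^7 = 30%.

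**5. Room for covariates.** With 40 per arm and 50% vs 70%, responders number 40 × 0.5 + 40 × 0.7 = 48 and non-responders 80 - 48 = 32. Arm plus three covariates uses four parameters, or 32 / 4 = 8 non-responders per parameter. A two-level MRI factor brings this to 32 / 5 = 6.4. The list has to be short.

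**The case against.** The unadjusted test is a legitimate choice. It holds its type I error, and adjustment is a refinement. That stands: the loss is in precision, not validity. The gain also depends on assumptions. At the weaker covariate strength it is about 2 points, and nothing in the documents shows that pain duration, MRI diagnosis or baseline NRS predicts 50% response. Entry at NRS 4 or higher narrows the range of that score. This limits the size of the benefit, but the simulations show no material penalty if the covariates prove useless.

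A reader might infer four stronger points that the documents do not support:

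- *That the plan states it will test baseline differences.* The section never uses the word baseline. Its first sentence is descriptive and includes satisfaction, which is recorded only after injection. The test rule could be meant for outcomes alone. Baseline testing is the natural reading of adjacent sentences, but it remains an inference.
- *That a spurious baseline difference is likely.* The 46% is close to a ceiling, because it needs all 12 items to be tested and independent. Height, weight and sex are plausibly correlated, as are the pain and disability scores.
- *That the primary result will be biased by adjustment chosen after seeing the data.* No section plans this. The plan is silent on what follows an imbalance, which leaves the possibility open and no more.
- *That the baseline data play no part in the main answer.* Baseline neck and arm NRS are the denominators of the percentage reduction, and patient traits enter the effect-modifier model. Neither use adjusts the treatment comparison.

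**Conclusion.** The point holds as a worthwhile improvement to a valid analysis. The primary comparison is unadjusted, and the baseline values already collected are not used to sharpen it. At 50% vs 70% and 40 per arm, pre-specified adjustment takes power from about 45% to about 48-55%. Across all scenarios with a prognostic covariate the gain is about 2 to 12 points. It is essentially zero, with no material loss, when the covariate is not prognostic. Adjustment makes the trial somewhat more informative; it does not make it well powered for a 20-point difference.

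On the natural reading, the plan also tests baseline variables between randomised arms. Those p-values carry no useful information, and at least one would fall below 0.05 in about 27-43% of trials if the 12 items are correlated (assumed rho 0.6 to 0.2), and in at most about 46% if independent.

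Alpha, response rates, covariate strength and correlations are all assumptions, because the documents give none.

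**What to change.** Make two changes in the Statistical analysis section.

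1. Pre-specify the primary analysis as logistic regression of 1-month responder status on arm plus a short fixed list of covariates, included whatever the observed balance. An example is baseline neck NRS, baseline arm NRS and pain duration. Report a standardised risk difference with 95% CI, which keeps the result on the scale of the difference in responder proportions. Keep the unadjusted chi-square or Fisher test as supportive. Include MRI diagnosis only as a pre-defined two-level factor, such as herniation versus stenosis. The Introduction attributes 21.9% and 68.4% of cases to these causes, which leaves 100 - 21.9 - 68.4 = 9.7%, so the plan needs a rule for patients in neither group or in both.
2. State that baseline characteristics are presented by arm without hypothesis tests, and that the between-group tests apply to outcomes only.

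The cost is a few sentences and a slightly more complex analysis. No new data are needed.

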#### Inclusion Criteria:

- 1) Age 18-80.
- 2) Clinical diagnosis of unilateral C4-C8 radicular pain.
- 3) Magnetic resonance imaging pathology consistent with clinical symptoms/signs.
- 4) Numerical Rating Scale (NRS) pain score of 4 or higher.
- 5) Pain duration of more than 6 weeks despite trial of conservative therapy (medications, physical therapy, or chiropractic care).

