## **Power Analysis**

Size of study groups: 40; 80 total participants.

The necessary sample size was determined based on a review of past literature and power analysis. While no head-to-head studies of targeted approaches to ESI have been performed in the cervical spine, such studies have been conducted in the lumbar spine. Studies that used sample sizes of 20-30 participants per treatment group showed statistically significant differences ( $P < 0.05$ ). We will thus plan to recruit 100 participants (50 per group) in anticipation of a 20% attrition rate by 6-month follow-up, which would still result in approximately 40 participants per group, to allow for improved power to detect a difference between groups compared to the prior cited similar literature.

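### Five numerical secondary outcomes have a baseline that the planned t test does not adjust for, and the median NRS outcome has no matching summary or test

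*Combined protocol and SAP*

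**What the plan says.** Under Data Collection the protocol states "Before an initial injection, the following measures will be obtained" and lists neck NRS, arm NRS, NDI-5, MQS III and daily opioid use. It then states "At intervals of 2 weeks, 1 month, 3 months, 6 months, and 1 year after injection, outcome measurements will be repeated". PGIC and satisfaction are recorded at follow-up only.

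The Data Analysis Plan says "Secondary outcomes included reduction in median NRS pain score (both neck pain and arm pain), NDI-5, MQS III, opioid consumption in daily morphine equivalents", then adds PGIC and satisfaction. The primary outcome is a responder proportion at 1 month.

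The Statistical analysis section gives one summary rule, "Means and standard deviations of subject demographic data, as well as pain, functional, and treatment satisfaction scores will be calculated", and one comparison rule, "Intergroup differences will be assessed by t test for numerical data and Chi Square or Fisher Exact test for categorical data". Its only modelling sentence begins "Regression modeling will be implemented using ANOVA to assess for patient traits and characteristics that increase the likelihood of efficacy using one technique".

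**The concern.** Two separate things look wrong.

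**Baseline is collected but not used in the arm comparison.** Five secondary outcomes have a pre-injection value. The t test could be run on follow-up scores, which ignores that value, or on change scores, which subtracts it with a fixed slope of 1. The word for reduction in the Data Analysis Plan points to change scores, but the Statistical analysis section does not confirm this. The same list also contains PGIC and satisfaction, for which no change score exists. Neither version is baseline-adjusted. The regression sentence asks which patients do better with which technique; it does not adjust the comparison of the arms.

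**The NRS outcome and its analysis do not match.** A t test compares means. An outcome defined by the median has no planned summary and no planned test, and it could mean either a difference between group medians or a median of individual changes. Left open, that choice could be made after the data are seen.

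At stake is precision on the secondary outcomes in a small trial, and a clear definition of the NRS outcome. The validity of the comparison is not in question.

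**Working it through.** **The plan's own figure.** The Power Analysis gives 40 per group after 20% attrition: 40 / (1 − 0.20) = 50 per group, 100 in total. This reproduces. The 40 itself cannot be derived, because no effect size, SD, event rate, power or alpha is stated for the trial.

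**Inputs**
- From the documents: n = 40 per arm, from "in anticipation of a 20% attrition rate by 6-month follow-up, which would still result in approximately 40 participants per group". This is the 6-month figure; earlier visits may retain more.
- Assumed: two-sided alpha 0.05; true difference d = 0.5 follow-up SD; baseline to follow-up correlation ρ = 0.3, 0.5, 0.7; SD ratio k = SD(baseline) / SD(follow-up) = 1.0, 0.8, 0.7.
- Why k below 1 is included: entry requires "Numerical Rating Scale (NRS) pain score of 4 or higher", which narrows the baseline spread (the criterion does not say whether neck or arm). As an illustration, an assumed normal NRS with mean 5 to 6 and SD 2 to 2.5, rounded, limited to 0–10 and cut at 4, keeps 0.71 to 0.82 of its SD.

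**Variance of the arm comparison, in follow-up-SD units**
- Follow-up t test: 1
- Change-score t test: 1 + k² − 2ρk
- ANCOVA: 1 − ρ²

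Change minus ANCOVA is k² − 2ρk + ρ² = (k − ρ)². Follow-up minus ANCOVA is ρ². Neither can be negative, so ANCOVA is never less precise than either t test, apart from one degree of freedom and a small allowance for chance baseline imbalance. The change-score test is worse than ignoring baseline when ρ < k/2, that is below 0.50, 0.40 and 0.35 at k = 1.0, 0.8 and 0.7.

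Example at ρ = 0.5: ANCOVA 1 − 0.25 = 0.75. Change at k = 1.0 is 1 + 1 − 1 = 1.00; at k = 0.8 it is 1 + 0.64 − 0.80 = 0.84. Since 40 × 0.75 = 30, about 30 per arm with ANCOVA match 40 per arm with the follow-up t test.

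**Power** (noncentral t, noncentrality d / √(2 × variance / 40), df 78 for the t tests and 77 for ANCOVA)

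| Analysis | ρ = 0.3 | ρ = 0.5 | ρ = 0.7 |
|---|---|---|---|
| Follow-up t test | 59.8% | 59.8% | 59.8% |
| Change, k = 1.0 | 46.3% | 59.8% | 81.4% |
| Change, k = 0.8 | 53.6% | 67.4% | 86.5% |
| Change, k = 0.7 | 57.0% | 70.0% | 87.1% |
| ANCOVA | 63.9% | 72.2% | 87.1% |

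**ANCOVA's gain in percentage points**

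| Compared with | k | ρ = 0.3 | ρ = 0.5 | ρ = 0.7 |
|---|---|---|---|---|
| Better t test | 1.0 | 4.0 | 12.4 | 5.8 |
| Better t test | 0.8 | 4.0 | 4.9 | 0.6 |
| Better t test | 0.7 | 4.0 | 2.2 | 0.0 |
| Change score | 1.0 | 17.6 | 12.4 | 5.8 |
| Change score | 0.8 | 10.3 | 4.9 | 0.6 |
| Change score | 0.7 | 6.9 | 2.2 | 0.0 |

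Allowing for chance baseline imbalance (variance factor 1 + 1/(2n − 4) = 1 + 1/76), ANCOVA power becomes 63.3%, 71.7% and 86.7%. The gain over the better t test then ranges from 11.9 points (k = 1.0, ρ = 0.5) to −0.4 (k = ρ = 0.7). A simulation of 8,000 runs per setting agrees with these figures to within about a point and a half.

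**Interval width, which does not depend on d.** At ρ = 0.5 the 95% CI half-width is 0.445 SD for the follow-up test; 0.445, 0.408 and 0.396 for change at k = 1.0, 0.8 and 0.7; and 0.386 for ANCOVA.

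**The median.** This needs no arithmetic. The Data Analysis Plan names a median; the Statistical analysis section plans means, SDs and t tests. No median, rank or quantile method appears anywhere in the document.

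**The case against.** The strongest reply is that this is a preference for efficiency, not an error. The t test is unbiased under randomisation, the primary outcome is a proportion, and baseline already enters the responder definitions for NDI-5 and MQS III. That is right, and it caps the grade: this is an improvement the plan should make, not a flaw that invalidates it.

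The second reply is that the size rests on assumptions. This also stands. At k = 1.0 and ρ = 0.5, with the imbalance allowance, the gain over the better t test is about 7 points at d = 0.3, 12 at 0.5, 9 at 0.65 and 4 at 0.8, so 12 points is close to the peak. For NRS, where k below 1 is plausible, the gain over the better t test is 0 to 5 points. Opioid dose may be skewed or full of zeros, where normal-theory power need not apply.

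A third reply is that an entry floor lowers ρ as well as k, so the grid should not treat them as independent. It should indeed be read as a range. But if the floor leaves the regression slope ρ/k unchanged, moving from k = 1.0, ρ = 0.5 to k = 0.8, ρ = 0.4 gives a change-score variance of 1 + 0.64 − 0.64 = 1.00 against 0.84 for ANCOVA. The gain shrinks but does not vanish. The two are equal only when the slope is 1.

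Finally, the median could be deliberate, since NRS is bounded, and the documents could be reconciled in that direction instead. They could, but that would need a new summary and a new test, whereas the mean fits the analysis already planned. None of this removes either point.

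**Conclusion.** Both points hold. The five numerical secondary outcomes with a baseline are to be compared by an unadjusted t test, and the NRS outcome as named has no matching summary or test.

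The first is a loss of precision only. Under the assumptions shown, ANCOVA gains from nil to 12 points of power over the better t test, and from nil to 18 points over the change-score test that the wording suggests. The 12-point figure needs equal SDs, ρ = 0.5 and d = 0.5; the gain disappears when k is close to ρ. The case for acting is that ρ and k are not known in advance. ANCOVA is best, or within half a point of best, in every setting shown, while each t test can lose materially. The mismatch over the median rests on the text alone. The binary primary outcome, PGIC and satisfaction are unaffected.

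**What to change.** For neck NRS, arm NRS, NDI-5, MQS III and daily opioid dose, replace the t test with one of these, chosen in advance:
- ANCOVA at a named visit, with arm and that outcome's baseline value; or
- a mixed model over visits with arm, visit, arm-by-visit and baseline, with the visit of main interest named. At present a visit is fixed only for the primary outcome.

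Report the adjusted mean difference with its 95% CI. With baseline in the model the arm estimate is the same whether follow-up or change is the response, so that ambiguity goes away.

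In the Data Analysis Plan, define the NRS outcome as a mean reduction, in line with the planned means and t tests, and keep medians and IQRs as description. If the sponsor wants the median, the summary and the test must change to match. Add a robust or rank-based sensitivity analysis for opioid dose. Keep chi-square or Fisher for the binary outcomes.

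The cost is SAP wording only: no new data, visits or participants.
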